Appendix F. Static Physician Global Assessment (sPGA)

The sPGA is a 5 point score ranging from 0 to 4, based on the physician's or representative's assessment of the average thickness, erythema, and scaling of all psoriatic lesions. The assessment is considered "static" which refers to the subject's disease state at the time of the assessments, without comparison to any of the subject's previous disease states, whether at baseline or at a previous visit.

A lower score indicates less body coverage, with 0 being clear and 1 being almost clear.

Erythema (0) Normal (Post-inflammatory hyperpigmentation may be present)

- (1) Pink coloration of lesions
- (2) Light red coloration of lesions
- (3) Dull to bright red coloration of lesions
- (4) Bright to Deep red coloration of lesions

Induration (0) None

- (1) Just detectable
- (2) Mild thickening
- (3) Clearly distinguishable to moderate thickening
- (4) Severe thickening with hard edges

Scaling (0) No scaling

- (1) Minimal focal scaling
- (2) Predominately fine scaling
- (3) Moderate scaling
- (4) Severe/coarse scaling covering almost all or all lesions

Scoring: a composite score is generated from the above data and the final sPGA is determined from this composite score as follows:

Clear	0 = 0 for all three
Almost clear	1 = mean > 0, < 1.5
Mild	2 = mean >= 1.5, < 2.5
Moderate	3 = mean >= 2.5, < 3.5
Severe	4 = mean >= 3.5

sPGA Rating Scale for Overall Psoriatic Disease

Score	Short Description	Detailed Description
0	clear	No signs of psoriasis. Post-inflammatory hyperpigmentation may be present
1	Almost clear	Normal to pink coloration; No thickening No to minimal focal scaling
2	mild	Pink to light red coloration Just detectable to mild thickening Predominantly fine scaling
3	moderate	Dull to bright red coloration Clearly distinguishable to moderate thickening Moderate scaling
4	severe	Bright to deep dark red coloration; Severe thickening with hard edges Severe coarse scaling covering almost all or all lesions

[figure not shown]
Appendix G. Nail Psoriasis Severity Index (NAPSI)

The nails will be graded for nail matrix psoriasis and nail bed psoriasis. The sum of the two scores is the total score for that nail.¹⁸

Nail Matrix Psoriasis

The Nail Matrix Psoriasis consists of any of the following: pitting, leukonychia, red spots in the lunula, and nail plate crumbling.

Score for Matrix Psoriasis

	
0 = none
 
1 = present in 1 quadrant of nail
 
2 = present in 2 quadrants of nail
 
3 = present in 3 quadrants of nail
 
4 = present in 4 quadrants of nail

--	--

Nail Bed Psoriasis

The Nail Bed Psoriasis is the presence or absence of any of the following: onycholysis, splinter hemorrhages, oil drop (salmon patch) discoloration, and nail bed hyperkeratosis.

Score for Nail Bed Psoriasis

	
0 = none
 
1 = present in 1 quadrant of nail
 
2 = present in 2 quadrants of nail
 
3 = present in 3 quadrants of nail
 
4 = present in 4 quadrants of nail

---	--

The sum of the scores will be added resulting a range of 0 to 80. If an individual finger assessment is missing (not done), the average of the remaining measured digits will be imputed and added to the sum. If < 50% of the finger assessments are missing the imputation will be performed. If more than 50% of the assessments are missing then the sum of the scores will be left as missing.

Appendix H. Palmoplantar Psoriasis Area and Severity Index (PPASI)

The PPASI provides a numeric scoring for psoriasis affecting the hands and feet with scores ranging from 0 to 72. It is a linear combination of percent of surface area of hands and feet that are affected and the severity of erythema, induration, and desquamation.

If a subject has palmoplantar psoriasis, the physician will assess the psoriasis at each protocol defined time point. Both palms and soles on each hand and foot will be individually assessed for erythema, induration, desquamation and percentage of area affected as follows:

- Erythema, Induration and Desquamation:

0 = None

1 = Slight

2 = Moderate

3 = Severe

4 = Very Severe

- Percent of Palm and Sole Area Covered:

0 = Clear

1 = < 10%

2 = 10 – 29%

3 = 30 – 49%

4 = 50 – 69%

5 = 70 – 89%

6 = 90 – 100%

The PPASI is a composite score and will be computed for each palm and sole, left and right and is derived from the sum of the scores for erythema (E), induration (I) and desquamation (D) multiplied by the score recorded for the extent of palm and sole area involved. PPASI is calculated as follows: (sum of scored for E+I+D)*Area

*0.2(location: right palm) + (sum of scored for E+I+D)*Area *0.2(location: left palm) +
(sum of scored for E+I+D)*Area *0.3(location: right sole) +(sum of scores for
E+I+D)*Area *0.3(location: left sole). The range is 0 to 72.

Appendix I. Psoriasis Scalp Severity Index (PSSI)

If a subject has scalp psoriasis, the physician will assess the erythema (redness), induration (hardness), desquamation (shedding of skin) and percent of scalp covered at each protocol defined time point.

Erythema, Induration and Desquamation:

- 0 = None
- 1 = Slight
- 2 = Moderate
- 3 = Severe
- 4 = Very Severe

Percent of Scalp Covered:

- 1 = < 10%
- 2 = 10 – 29%
- 3 = 30 – 49%
- 4 = 50 – 69%
- 5 = 70 – 89%
- 6 = 90 – 100%

The PSSI is a composite score derived from the sum of the scores for erythema, induration and desquamation multiplied by the score recorded for the extent of scalp area involved. The range is 0 to 72.

Appendix J. Dermatology Life Quality Index (DLQI)

The DLQI has been extensively used in clinical studies and has a large evidence base supporting reliability and validity.¹⁹ The DLQI is a self-administered, ten-question questionnaire used to assess the effect of different skin diseases on a subject's quality of life, overall health, and disability status.²⁰ The questionnaire covers six domains including symptoms and feelings, daily activities, leisure, work and school, personal relationships and treatment and has a 1-week recall period.¹⁵

Each item is scored on a 4 point scale where a 0 score indicates "not relevant/not at all," and scores from 1 to 3 range from "a little," to "very much." Question 7 is a "yes"/"no" question where "yes" is scored as 3. If Question 7 is answered "no," scores range from 0 ("not at all") to 2 ("a lot").²¹

The DLQI total score is calculated by summing the scores of each question, resulting in a range of 0 to 30 where 0 – 1 = "no effect on subject's life," 2 – 5 = "small effect," 6 – 10 = "moderate effect," 11 – 20 = "very large effect," and 21 – 30 = "extremely large effect on subject's life." The higher the score, the more the quality of life is impaired. A 4-point change from baseline is considered a clinically important difference.²⁰

The DLQI will be analyzed under six headings as follows:¹⁷

Domain	Question Number	Score
Symptoms and feelings	Questions 1 and 2	Score maximum 6
Daily activities	Questions 3 and 4	Score maximum 6
Leisure	Questions 5 and 6	Score maximum 6
Work and school	Question 7	Score maximum 3
Personal relationship	Questions 8 and 9	Score maximum 6
Treatment	Question 10	Score maximum 3

3.0 Introduction

This statistical analysis plan (SAP) describes the statistical analysis to be completed by the AbbVie Clinical Statistics Department for study Protocol M15-997 Amendment 8 dated 18 October 2021.

This SAP will provide details to further elaborate statistical methods as outlined in the Protocol M15-997 and will describe analysis conventions to guide the statistical programming work. The SAP will be signed off before the study database is locked.

Analyses will be performed using SAS[®] version 9.4 (SAS Institute, Inc., Cary, NC 27513) or higher using the UNIX operating system.

4.0 Study Objectives, Design and Procedures

4.1 Primary Study Objective

The primary objective of Study M15-997 is to investigate long-term safety and tolerability of risankizumab in subjects with psoriasis who have completed one of the preceding Phase 2/3 studies.

[figure not shown]
The secondary objective of Study M15-997 is to investigate the long-term efficacy of risankizumab in the treatment of psoriasis.

4.2 Design Diagram

This is a Phase 3, single-arm, multicenter, OLE study designed to investigate the long term safety and efficacy of risankizumab 150 mg E12W in the treatment of moderate to severe chronic plaque psoriasis. Approximately 2200 subjects who meet the entry criteria are planned to be enrolled in this study, rolling over from the preceding Studies 1311.3, 1311.4, 1311.13, 1311.28, 1311.30, 1311.38, and M16-178 (Phase 2/3, randomized clinical studies in subjects with moderate to severe chronic plaque psoriasis, conducted by Boehringer Ingelheim or AbbVie).

All subjects need to complete one of the preceding Phase 2/3 psoriasis studies. The subject preferably has the Baseline visit of Study M15-997 on the same day of the completion visit of the preceding study; however, the Baseline visit can be delayed up to 8 weeks if needed. All subjects will be administered 150 mg risankizumab s.c. at the Baseline visit, and from the Baseline visit onwards, risankizumab will be administered subcutaneously E12W during the study. Study visits for dosing, efficacy and safety assessments will be performed E12W starting from Baseline until the Week 156 visit. After this visit until the End of Treatment (EOT) visit at Week 252, study visits will be performed E24W. The schematic of the study is shown in [Figure 1](#).

Figure 1. Study Schematic

There is a ± 7 days visit window for study visits. Every effort will be made to bring subjects back to their original scheduled visit (calculated from Baseline) if they are out of the visit window. Subjects who discontinue study drug treatment early will need to attend an early EOT visit ideally within 2 weeks after the decision and preferably prior to the administration of any new therapies.

All subjects, including those that prematurely discontinued study drug treatment, will return to the clinic for an End of Observation Visit (EOO) 20 weeks after their last administered dose of risankizumab. Study completion is defined as a subject having completed the EOO visit.

4.3 Sample Size

The sample size is determined by the completion of preceding studies and the consenting for the extension.

Multiple clinical studies will be rolling into this OLE study. Eligible subjects from Studies 1311.3, 1311.4, 1311.13 (extension study of 1311.2), 1311.28, 1311.30, 1311.38, and M16-178 will be offered participation in this OLE study at their respective or referring sites. The check for subject eligibility will be based upon a successful completion of the preceding study, signing the informed consent for this study, and the other inclusion and exclusion criteria.

A 10% to 15% dropout rate from preceding studies is expected, leaving approximately 2200 subjects to be entered in this study.

4.4 Interim Analysis

The first interim analysis was performed in 2017, after the last patient in Study 1311.4 either had completed Week 52 visit or discontinued from the study, and at the time approximate to the database lock of all other preceding studies, whichever occurs later, to generate sufficient evidence for long-term safety and efficacy of risankizumab in subjects with psoriasis.

To support regulatory activities in Switzerland, a second interim analysis will be conducted to include all available patient data up to the data cut-off date of November 01, 2021.

Additional interim analyses may be performed based on regulatory or other requirements.

5.0 Analysis Populations

Subjects are required to have at least one dose of risankizumab in Study M15-997 to be included in any of the analysis populations.

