- If the subject experiences an intolerable increase of psoriasis during the course of the study the subject will be discontinued from the study drug to receive rescue treatment as deemed appropriate by the investigator.
- If the subject experiences a serious infection, the study drug should be held until the infection is resolved or stabilized. The study drug dosing visit could

be postponed such that the study drug of the following visit will not be administered within 14 days. If the subject has not received study drug due to this serious infection for at least 24 weeks, the subject will be permanently withdrawn from study drug.

If, during the course of study drug administration, the subject prematurely discontinues study drug use, the subject has the option to continue in the study and complete the remaining visits as scheduled. If remaining visits will be completed, an early EOT visit is not required. If the subject does not continue in the study, the procedures outlined for the early EOT visit must be completed, ideally within 2 weeks of the decision and preferably prior to the initiation of another therapy. However, these procedures should not interfere with the initiation of any new treatments or therapeutic modalities that the Investigator feels are necessary to treat the subject's condition. For subjects that prematurely discontinue, study drug will not be given at the early EOT visit and subjects should have the telephonic EOO visit, 20 weeks after their last administered dose of study drug to determine the status of any ongoing AEs/SAEs or the occurrence of any new AEs/SAEs.

Following discontinuation of the study drug, the subject will be treated in accordance with the Investigator's best clinical judgment.

All attempts must be made to determine the primary reason for premature discontinuation. The information will be recorded on the appropriate eCRF page.

For subjects that are considered lost to follow-up, reasonable attempts must be made to obtain information on the final status of the subject. At a minimum, two phone calls must be made and one certified letter must be sent and documented in the subject's source documentation.

Interruption/Discontinuation of Study Drug Due to COVID-19

For subjects with documented COVID-19, the timing of next administration of study drug or possibility of premature discontinuation from study drug should be discussed with the AbbVie Medical Contact.

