9.0 Study Drug Exposure and Compliance

Study drug exposure (days) will be summarized using the sample size, mean, standard deviation, minimum, median and maximum. Study drug exposure will be summarized as follows:

Risankizumab Exposure (in Days):

The Risankizumab Exposure (total duration during the preceding study and Study M15-997) will be defined as follows:

The Risankizumab Exposure = Last risankizumab dose date – First risankizumab dose date (either in Study M15-997 or preceding study) + 84 days, except:

- The Risankizumab Exposure in the Retreatment Population is defined as: Last risankizumab dose date – First retreatment of risankizumab date (either in Study M15-997 or preceding study) + 84 days
- The Risankizumab Exposure in the ALL_RZB Population among subjects who were re-randomized to placebo during Study 1311.4 Part B is defined as: Last risankizumab dose date during Study 1311.4 Part A – First risankizumab dose date + 84 days + Last risankizumab dose date – First retreatment of risankizumab date + 84 days

In addition, number of subjects who have at least one dose of self-injected study drug during Study M15-997 will also be summarized.

A data cutoff date (September 01, 2017) was applied during the first interim analysis in 2017.

A data cutoff date (November 01, 2021) will be applied during the second interim analysis. The duration of study drug exposure will be defined up to this cutoff date.

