11.2 Analysis of Adverse Events

11.2.1 Treatment-Emergent Adverse Events

Treatment emergent adverse events (TEAEs) are defined as any event with an onset date that is after the first dose of risankizumab and with an onset date within 140 days after the last dose of study drug in the analysis period except:

- **TEAE of Retreatment:** TEAE are defined as any event with an onset date that is after the first dose of retreatment and no more than 140 days after the last dose of study drug, and prior to the start of risankizumab 75 mg (if any, for subjects in Japan).
- **TEAE of ALL_RZB (any dose):** TEAEs are defined as any event with an onset date after the first dose of risankizumab through 140 days after the last dose of risankizumab, except for AEs with an onset date during protocol-designed treatment gaps (i.e., placebo period in subjects re-randomized to placebo during Study 1311.4 Part B) that was more than 140 days from the last dose of previous risankizumab treatment and before the first dose of retreatment in the ALL_RZB Population.
- **TEAE of RZB, RZB_NL, UST_RZB, ADA_RZB, FUM_RZB and ALL_RZB (150 mg):** TEAEs are defined as any event with an onset date after the first dose of risankizumab 150 mg through 140 days after the last dose of risankizumab 150 mg, and prior to the start of risankizumab 75 mg (if any, for subjects in Japan), except for AEs with an onset date during protocol-designed treatment gaps (i.e., placebo period in subjects re-randomized to placebo during Study 1311.4 Part B) that was more than 140 days from the last dose of

previous risankizumab 150 mg treatment and before the first dose of retreatment in the ALL_RZB Population.

Events where the onset date is the same as the study drug start date are assumed to be treatment emergent, unless the adverse event start time is prior to the study drug start time. If an incomplete onset date is collected for an adverse event, the event will be assumed to be treatment-emergent unless there is other evidence that confirms that the event is not treatment-emergent (e.g., the event end date is prior to the study drug start date).

The number and percent of subjects experiencing treatment-emergent TEAEs will be tabulated using the Medical Dictionary for Drug Regulatory Activities (MedDRA[®]) system organ class and preferred term.

Summary tables will be presented as follows:

1. Adverse Event Overview

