The number and percentage of subjects experiencing treatment-emergent adverse events will be summarized for the following adverse event categories:

- Any AE
- Any AE that was assessed as related to study drug by the investigator
- Any severe AE
- Any serious AE
- Any serious AE that was assessed as related to study drug by the investigator
- Any AE leading to discontinuation of study drug
- Any AE leading to death
- Any deaths
- Areas of Safety Interest
- Any COVID-19 Related AE

2. Adverse Events by System Organ Class and Preferred Term

TEAEs will also be summarized and presented using primary Medical Dictionary for Regulatory Activities (MedDRA) system organ classes (SOCs) and preferred terms (PTs). The SOCs will be presented in alphabetical order, and the PTs will be presented in alphabetical order within each SOC.

Subjects reporting more than one adverse event for a given MedDRA preferred term will be counted only once for that term (most severe incident for the severity tables and most related incident for the relationship tables). Subjects reporting more than one type of adverse event within a SOC will be counted only once for that SOC. Subjects reporting more than one type of adverse event will be counted only once in the overall total.

In addition, the number and percentage of adverse events with causal relationship between the events and the study drug will be summarized using the same conventions described above.

3. Adverse Events by Maximum Severity

The severity grading of AEs follows Rheumatology Common Toxicity Criteria (RCTC).

- Grade 1 – mild
- Grade 2 – moderate
- Grade 3 – severe
- Grade 4 – life threatening

Adverse events will also be summarized by maximum severity. If a subject has an adverse event with unknown severity, then the subject will be counted in the severity category of "unknown," even if the subject has another occurrence of the same event with a severity present. The only exception is if the subject has another occurrence of the same adverse event with the most extreme severity – ("Life-threatening"). In this case, the subject will be counted under the "Life-threatening" category.

4. Adverse Events by Maximum Relationship

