Serious Infections	Serious AEs in the Infections and Infestations SOC	
Active Tuberculosis	Active Tuberculosis CMQ (code 80000188)	
Opportunistic Infections excluding tuberculosis and herpes zoster	Opportunistic infection excluding tuberculosis and herpes zoster CMQ (code 80000189)	
Injection Site Reactions	Narrow	Injection site reaction CMQ (code 80000019)
Malignancies	Narrow	Malignant tumours (SMQ 20000194)
Non-melanoma Skin Cancer (NMSC)	Broad	Skin malignant tumours (SMQ 20000204) excluding terms identified by the Melanoma CMQ (code 80000119)
Malignant Tumours excluding NMSC	'Malignant Tumours excluding NMSC' is identified by the 'Malignant Tumours' search excluding terms identified by the 'Non-melanoma skin cancer (NMSC)' search.	
Hypersensitivity	Narrow	Hypersensitivity (SMQ 20000214)
Serious hypersensitivity reactions	Narrow	Serious AEs in the Hypersensitivity (SMQ 20000214)
Adjudicated Anaphylactic Reaction*	Adjudicated terms will be identified using SDTM data (e.g., CE and PR domains).	
Hepatic Events	Broad	Hepatic failure, fibrosis and cirrhosis and other liver damage-related conditions (SMQ 20000013)
	Broad	Hepatitis, non-infectious (SMQ 20000010)
	Broad	Cholestasis and jaundice of hepatic origin (SMQ 20000009)
	Broad	Liver related investigations, signs and symptoms (SMQ 20000008)
	Narrow	Liver-related coagulation and bleeding disturbances (SMQ 20000015)

* Events will be identified for adjudication by Anaphylactic Reaction SMQ Broad search as specified in the RISA AAC Charter.

Adverse Event per 100 Patient-Years of Exposure

Adverse events occurring during the analysis period for each population will be presented by event rate per 100 patient-years. These will be presented for any TEAEs, serious adverse events, Areas of Special Interest.

AEs per 100 patient-years of exposure is defined as the number of AEs divided by the total exposure in 100 patient-years. Note that one event per preferred term per day per subject will be counted in the calculation of the number of AEs (i.e., a preferred term will not be counted twice on the same day for the same subject). See the calculation method below.

$$100 \times \frac{\text{Number of TEAEs}}{\text{Total Patient Years}}$$

where total patient years is defined as the sum of the study drug exposure (defined as date of last dose – date of first dose + 140 days (5 half-lives)) of all subjects normalized by 365.25, and rounded to one decimal place.

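### Rates per 100 patient-years count preceding-study time that is conditional on roll-over, so rates of death and malignancy excluding NMSC understate the extension-period rates

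*SAP*

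**What the plan says.** **Who is analysed.** SAP 5.0: "Subjects are required to have at least one dose of risankizumab in Study M15-997 to be included in any of the analysis populations". Protocol 5.2.1 and 5.2.2 decide who can reach that dose. The subject must have completed the preceding study. Exclusions include premature discontinuation from it, active or suspected malignancy arising during it (treated basal or squamous cell skin carcinoma and in situ cervical carcinoma are exempt), and TB unless work-up rules out active disease.

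**When the clock starts.** For ALL_RZB at any dose, SAP 11.2.1 says "TEAEs are defined as any event with an onset date after the first dose of risankizumab through 140 days after the last dose of risankizumab". It gives a parallel 150 mg rule for RZB, RZB_NL and ADA_RZB, and starts Retreatment at the first retreatment dose. Protocol 8.1.5 confirms that the first risankizumab dose may lie in the preceding study.

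**What the rate divides by.** In SAP 11.2.1, "total patient years is defined as the sum of the study drug exposure", with exposure taken as last dose minus first dose plus 140 days.

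**Which rates are planned.** On event rates the SAP says: "These will be presented for any TEAEs, serious adverse events, Areas of Special Interest". Table 12 includes active TB and malignant tumours excluding NMSC. Separate rates for deaths and AE discontinuations are promised in protocol 8.1.5 but are not named in this SAP list.

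**The concern.** Membership of every population is decided at OLE entry, but the clock starts before it. Time between the first risankizumab dose and entry is counted only for subjects who went on to enter. A subject who died in that interval contributes neither the death nor the time. A subject who entered contributes the time with no possibility of a death. Numerator and denominator cover the same window, but that does not help, because the person-time was selected on the outcome.

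The affected groups are RZB, RZB_NL, ADA_RZB subjects switched at Week 16, Retreatment subjects retreated before the OLE, and ALL_RZB, which contains them. UST_RZB and FUM_RZB are not affected, because SAP Table 10 sets their Day 1 at M15-997 entry. Subjects switched or retreated only at OLE entry have no such lead-in within ADA_RZB and Retreatment.

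Long-term safety is the primary objective, and protocol 3.2 says that malignancy risk under long-term treatment is unknown. For the affected populations the SAP plans neither an OLE-period rate nor a caveat. No hypothesis is tested, so the consequence lies in the reported estimates and how they are read.

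**Working it through.** The documents give no event rate for these outcomes, so there is no planned figure to reproduce. The check concerns person-time.

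**Inputs**
- OLE dosing runs to Week 252 (protocol 5.1), and the rate window adds 140 days. Post-entry time is 252 × 7 + 140 = 1904 days.
- Lead-in is the label of the last PASI/sPGA window in the SAP minus 252. Where the 12-week spacing ends at a single point (Tables 1, 3 and 8), that label minus 156 gives the same answer.
  - RZB (Table 1): 304 − 252 = 52 weeks; 208 − 156 = 52.
  - RZB_NL (Table 3): 288 − 252 = 36; 192 − 156 = 36.
  - ADA_RZB switched at Week 16 (Table 8): 280 − 252 = 28; 184 − 156 = 28.
  - Relapsed Retreatment (Table 5): 292 − 252 = 40 at the longest. The 12-week spacing ends at Week 172R, which suggests 172 − 156 = 16 at the shortest.
- For Retreatment, the first dose in the rate formula is taken to be the first retreatment dose, as in its TEAE rule.

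**Formula.** Let E be the events after entry, with none before it. The integrated rate is E / (T_pre + T_OLE) and the OLE rate is E / T_OLE. Their ratio, OLE to integrated, is (T_pre + T_OLE) / T_OLE. It exceeds 1 whenever T_pre > 0, however the hazard changes over time. Any counted event before entry lowers the ratio, so these values are upper limits.

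| Group | Lead-in, days | Last dose Week 252 | Last dose Week 156 (illustration) |
|---|---|---|---|
| RZB | 364 | 2268/1904 = 1.19 | 1596/1232 = 1.30 |
| Relapsed Retreatment, longest | 280 | 2184/1904 = 1.15 | 1512/1232 = 1.23 |
| RZB_NL | 252 | 2156/1904 = 1.13 | 1484/1232 = 1.20 |
| ADA_RZB, Week 16 switch | 196 | 2100/1904 = 1.10 | 1428/1232 = 1.16 |

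The second scenario uses 156 × 7 + 140 = 1232 days. It is an assumption, because no OLE dropout rate is given.

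The lead-ins are maxima on the nominal schedule. Within RZB, 1311.30 subjects have 16 + 28 = 44 weeks, which gives 2212/1904 = 1.16. The shortest relapsed Retreatment lead-in gives 2016/1904 = 1.06. A delayed entry, allowed up to 8 weeks, would add at most 56/1904 = 0.03 to a subject's ratio.

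**ALL_RZB.** The mix of feeder studies is not given, so no ratio follows. Each 10 weeks of mean lead-in would add 70/1904 = 0.037 at Week 252.

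**Absolute size.** Suppose integrated RZB rates of 0.05, 0.5 and 1.0 per 100 patient-years (assumed, not in the documents). Multiplying by 1.191 gives 0.06, 0.60 and 1.19. The rate shells in SAP Appendix A print one decimal, so the first change would not show and the other two would read 0.6 and 1.2.

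**The case against.** The plan is open about what it does. Protocol 8.1.2 and SAP 6.0 state that preceding-study data are integrated, and SAP 5.0 states the M15-997 dose condition. An OLE-start rate is itself conditional on roll-over. In ALL_RZB it would mix subjects at their first risankizumab dose with others up to about a year into treatment. Choosing between the two rates is therefore partly a choice of estimand. That stands, and it is a reason to show both rather than let the OLE rates alone carry the long-term conclusions.

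By-subject listings of deaths, AE discontinuations and areas of safety interest are planned, so events could be separated by period. OLE patient-years would still be missing.

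Four stronger readings are tempting, and the documents do not support them.

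- **All four outcomes are impossible before entry.** Only death is. In situ cervical carcinoma is exempt from the malignancy exclusion. The TB criterion does not address disease that arose and resolved before entry. The SAP's discontinuation outcome is "Any AE leading to discontinuation of study drug", whereas the entry exclusion does not say whether drug or study discontinuation is meant. In M15-997 the two differ: after stopping drug, "the subject has the option to continue in the study and complete the remaining visits as scheduled". Whether the preceding studies allowed the same is not shown.
- **The expected dropout counts the missing risankizumab subjects.** SAP 4.3 says "A 10% to 15% dropout rate from preceding studies is expected, leaving approximately 2200 subjects to be entered in this study". That covers all causes and does not separate arms. Some feeder subjects were on placebo or active comparators, so the number who received risankizumab is unknown. An OLE-start rate would not recover them either.
- **SAP 9.0 shows what the ALL_RZB rate counts.** The definition beginning "The Risankizumab Exposure in the ALL_RZB Population among subjects who were re-randomized to placebo during Study 1311.4 Part B is defined as" belongs to the exposure summary, which adds 84 days. The rate denominator is defined separately in SAP 11.2.1.
- **All safety rates are affected.** Entry does not select in the same way on other SAEs, non-fatal MACE, serious infections, NMSC, hepatic events, hypersensitivity or injection site reactions.

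**Conclusion.** The point holds in a limited form. It is certain for deaths: the lead-in time cannot contain one. It is near certain for malignancy excluding NMSC, where the in situ cervical exemption is the stated gap. For AE discontinuation and active TB the same direction is likely but rests on preceding protocols not shown.

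The understatement of the OLE-period rate is bounded by the nominal-schedule ratios for dosing through Week 252: 1.19, about 1.15, 1.13 and 1.10 for RZB, relapsed Retreatment, RZB_NL and Week 16 ADA_RZB switchers. These assume the longest lead-in for each group and no counted event before entry. Earlier last doses raise them. The absolute effect is modest and may vanish at one decimal for very rare events. It is worth correcting because it runs in one direction, towards a more favourable rate, on outcomes central to the primary objective. The absence of deaths and AE discontinuations from the SAP rate list is a separate mismatch with protocol 8.1.5.

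**What to change.** In SAP 11.2.1, for RZB, RZB_NL, Retreatment, ADA_RZB and ALL_RZB:

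1. Add rates with patient-years starting at the first M15-997 dose and the end of each window unchanged. Count these events from that dose onward:
   - deaths, by date of death;
   - malignancy excluding NMSC, by onset date;
   - AE discontinuations, by date of study drug discontinuation;
   - active TB, by onset date.

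   Dating deaths and discontinuations this way keeps OLE outcomes of AEs that began in the preceding study.
2. Show these beside the integrated rates. Keep the integrated rates with the footnote: 'Preceding-study patient-time is conditional on completing that study and entering M15-997.'
3. Add deaths and AE discontinuations to the SAP rate list to match protocol 8.1.5.

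The cost is SAP wording, one footnote and one extra set of rate columns for four outcomes. No new data are needed. The added rates use less patient-time, so they will be less precise and somewhat less favourable.
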